Efficacy of Extracorporeal Shock Wave Therapy On Cervical Myofascial Pain Following

Neck Dissection Surgery

12-2-2020

Study Protocol

Objective: Cervical myofascial pain is one of the problems that contribute in chronic neck pain

following neck dissection surgery, so we aimed to investigate efficacy of extracorporeal shock

wave therapy (ESWT) on cervical myofascial pain in expression of decreasing pain and improving

cervical range of motion (ROM).

Design: This trial is a single blind randomized control experimental study.

Subjects: 46 patients with cervical myofascial pain following neck dissection surgery were

recruited in this trial and subdivided at random into two equal groups. ESWT Group: received

ESWT once a week for 4 weeks (0.25 ml/mm², 1000 shocks) plus topical none steroidal anti-

inflammatory drug (NSAID; 3 times /day for 4 weeks). Control Group: received only topical

NSAID.

Outcome measures: Pain assessment was measured by visual analogue scale (VAS) and pressure

algometry. Cervical range of motion device (CROM) was used for assessment of lateral flexion

and rotation of neck ROM for both sides. All measurements were collected before the beginning

of the study, after 2 weeks and at the trial termination (after 4 weeks).

Results: ESWT Group revealed significant improvement in all parameters at post I and II compared to control group (p < 0.001), while the control group revealed only a statistical decrease in VAS at post I without any statistical difference in pain threshold and neck ROM, however, there were statistical differences in all parameters at post II compared to pre-treatment and post I (p < 0.001).

Conclusion: Higher statistical results were achieved with ESWT without any side effects confirming the safety and efficiency of ESWT in cervical myofascial pain.

Subject characteristics:

The mean \pm SD of subjects' characteristics of both groups is illustrated in Table 1. There weren't statistical differences (p>0.05) in the mean of age, weight, height and sex distribution between groups.

Effect of treatment on rotation and side bending ROM, VAS and PTT:

Mixed MANOVA showed a significant interaction effect of treatment and time (Wilks' Lambda = 0.01, F (12, 30) = 227.55, p = 0.001, = 0.98). There was a significant main effect of time (Wilks' Lambda = 0.005, F (12, 30) = 489.27, p = 0.001, = 0.99). There was a significant main effect of treatment (Wilks' Lambda = 0.03, F (6, 36) = 162.55, p = 0.001, = 0.96). Table 2 and 3 showed descriptive statistics of rotation and side bending ROM, VAS and PTT and the statistical level of

comparison between groups as well as significant level of comparison between pre, post I and post II in each group.

Between group comparisons

Pre-trial evaluations revealed non statistical difference between both study and control groups in all measured variables (p > 0.05). A significant increment of neck rotation, and side bending ROM in both directions away and toward the operated side with a marked improvement of PPT was reported at post I and II in the study group compared to control group (p > 0.001). Moreover, there was a significant decrease in VAS of the study group at post I and at post II compared to control group (p > 0.001).

Within group comparison

Statistical improvements were reported in the rotation and side bending ROM in both directions away and toward the operated side and also in PPT in the study group at post II in comparison with pre-treatment and post I (p < 0.001); furthermore, a significant amelioration in the rotation and side bending ROM in both directions and PPT at post I compared with that pre-treatment (p < 0.001). There was a statistical diminution of VAS in the study group at post II compared to pre-treatment and post I (p < 0.001); and also, in VAS at post I in comparison with pre-treatment (p < 0.001).

There was no statistical difference in the rotation and side bending ROM in both directions and in PPT between pre-treatment and post I (p > 0.05) in the control group; However there was a statistical increase in the rotation and side bending ROM in both directions and also in PPT at post II in comparison with pre-treatment and post I (p < 0.001). There was a statistical decrease in VAS in the control group at post II compared with that at pre-treatment and post I (p < 0.001); as well in VAS at post I in comparison with pre-treatment (p < 0.001).

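### The week 2 Results add a contrast of within-arm significance that does not test a treatment difference, and the outcome-specific between-arm tests that could stand in its place are unadjusted for baseline and carry contradictory p-values

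*Combined protocol and SAP*

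**What the plan says.** The Results paragraph of the Study Protocol opens with a comparison of the arms: "ESWT Group revealed significant improvement in all parameters at post I and II compared to control group (p < 0.001"). The same sentence goes on to say that "the control group revealed only a statistical decrease in VAS at post I without any statistical difference in pain threshold and neck ROM", and then that controls did change on all parameters at post II. Post I and post II are the week 2 and week 4 visits.

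The detailed results, under the heading on the effect of treatment, give three layers:

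- **Omnibus tests.** "Mixed MANOVA showed a significant interaction effect of treatment and time (Wilks' Lambda = 0.01, F (12, 30) = 227.55, p = 0.001"), followed by a main effect of time and "There was a significant main effect of treatment (Wilks' Lambda = 0.03, F (6, 36) = 162.55, p = 0.001").
- **Between group comparisons.** The gain in ROM and PPT is called significant and "was reported at post I and II in the study group compared to control group (p > 0.001"). The VAS result is called significant with the same p > 0.001. Baseline differences are reported as p > 0.05.
- **Within group comparison.** In the ESWT arm, ROM and PPT at post I differ from pre-treatment with p < 0.001. For controls the p-value is given only as above 0.05: "There was no statistical difference in the rotation and side bending ROM in both directions and in PPT between pre-treatment and post I".

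Tables 2 and 3 are described as holding descriptive statistics and significance levels. Their contents are not in the text available for this review.

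**The concern.** For PPT and the four ROM measures, the reader is offered a week 2 contrast of p < 0.001 in one arm and p > 0.05 in the other. Linking words in the Results sentence make the control arm's non-significance part of the comparison, and nothing marks it as descriptive. Three things follow.

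1. Two within-arm p-values do not test the difference between arms. Each also mixes any treatment effect with natural course and regression to the mean.
2. A p-value above 0.05 in a small arm is not evidence of no change.
3. If the contrast is set aside, as it should be, the week 2 evidence for each outcome rests on the between-arm comparisons. The text describes these as comparisons of the arms at each visit, mentions no adjustment for baseline, quotes no estimate or interval, and prints p-values that contradict the Results paragraph.

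At stake is how firmly, and how precisely, an early effect on each outcome can be stated.

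**Working it through.** **Inputs.** From the Study Protocol, Subjects: "46 patients with cervical myofascial pain following neck dissection surgery were" "recruited in this trial and subdivided at random into two equal groups", so 46/2 = 23 per arm. From the detailed results: interaction F = 227.55 on (12, 30) and treatment F = 162.55 on (6, 36). Assumed, because the documents do not state them: two-sided alpha of 0.05 and paired t-tests within arms.

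**1. Reproducing the stated omnibus figures.** For two groups, Lambda = 1/(1 + F × df1/df2).
- Interaction: 1/(1 + 227.55 × 12/30) = 1/92.02 = 0.0109 (stated 0.01); p about 5e-26.
- Treatment: 1/(1 + 162.55 × 6/36) = 1/28.09 = 0.0356 (stated 0.03, which looks truncated); p about 1.5e-24.

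The stated F values therefore imply p-values far below the printed 0.001. The error degrees of freedom imply 30 + 12 + 1 = 43 and 36 + 6 + 1 = 43 patients analysed, not 46, so the number of controls may be slightly below 23.

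**2. What the omnibus tests cover.** The interaction combines six outcomes and two contrasts over three visits (6 × 2 = 12 numerator df). It shows that the arms' profiles differ somewhere. It does not say at which visit or on which outcome.

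**3. What p > 0.05 in 23 controls can exclude.** By the noncentral t distribution with n = 23, a true within-arm change of 0.427 SD (SD of the change) has 50% power and one of 0.611 SD has 80% power. Changes of those sizes would be non-significant in 50% and 20% of trials.

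**4. How often the reported within-arm pattern arises when both arms truly change equally.** Per outcome, P = P(ESWT p < 0.001) × P(control p > 0.05).

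| Within-arm power at 0.05 (n = 23) | P |
|---|---|
| 20% | 1.0% |
| 50% | 3.5% |
| 80% | 4.8% |
| 90% | 3.8% |
| Maximum over effect sizes | 4.9% |

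At n = 21 and n = 22 the maxima are 4.7% and 4.8%. A direct two-sided 5% test falsely favours ESWT in 2.5% of trials, so the maximum is about twice that. For at least one of five outcomes, treated as independent: 1 − (1 − 0.049)^5 = 22%. Correlation between outcomes would lower this.

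**5. Adding the direct test.** In 100,000 simulated trials with equal change, n = 23 per arm and about 50% within-arm power, a direct between-arm test at 0.05 rejected in 4.99%. The pattern in step 4 together with between-arm p < 0.001 occurred in about 0.03%.

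**6. The between-arm p-values side by side.** The Results paragraph gives p < 0.001 for all parameters at both visits. *Between group comparisons* gives p > 0.001 for ROM and PPT, and again for VAS, at the same visits. Both cannot be right.

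**The case against.** The strongest reply is that the trial already reports the right kind of test. The Results sentence begins with ESWT against control, and the interaction asks whether change over time differs between arms. Comparing randomised arms at a follow-up visit is also unbiased without baseline adjustment. All of this stands. A reader might infer from the control clause that the efficacy claim depends on within-arm p-values. The documents do not support that.

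A reader might also apply the generic error rate for such contrasts. With equal change and 50% to 80% within-arm power, ESWT alone is significant in 0.5 × 0.5 = 25% to 0.8 × 0.2 = 16% of trials per outcome. At least one of five independent outcomes then shows it in 1 − 0.75^5 = 76% to 1 − 0.84^5 = 58%. Those figures are for p < 0.05 against p > 0.05 and for any one outcome. The report gives p < 0.001 against p > 0.05 on all five, alongside direct tests. The generic figures do not describe this trial and should not be used against it.

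The p > 0.001 is most plausibly a reversed sign, since the results are called significant. It should not be read as showing that the between-arm tests failed. Nor does the text say that control treatment does nothing: it reports VAS improvement at week 2 and improvement on all parameters at week 4.

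The reply does not reach three things. The interaction isolates neither week 2 nor a single outcome. The tests that do have conflicting printed p-values. And non-significance in about 23 controls is set beside the ESWT result without a descriptive label.

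**Conclusion.** The point holds as one about estimating and presenting the week 2 evidence. The within-arm contrast on PPT and four ROM measures tests no treatment difference and should carry no weight as efficacy evidence. The direct week 2 tests by outcome need a consistent p-value, a baseline-adjusted estimate and an interval.

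The size is modest. With equal true change, the reported within-arm pattern has a probability of at most about 4.9% per outcome, and about 0.03% once between-arm p < 0.001 is also required (simulated at about 50% within-arm power). These figures assume paired t-tests, two-sided 0.05, normal data and 23 per arm. The 0.03% also relies on p < 0.001 being the correct printing. Without the contents of Tables 2 and 3, the individual week 2 contrasts cannot be recomputed, and it cannot be judged whether the tables already give between-arm estimates. If the stated F values are right, nothing here casts doubt on an overall difference between the arms.

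**What to change.** - For each of the six outcomes at weeks 2 and 4, report the ESWT minus control difference adjusted for the baseline value, with 95% CI and p-value. An analysis of covariance at each visit, or a repeated-measures model with baseline as covariate, would do.
- Check the between-group p-values against the analysis output, and make the Results paragraph and *Between group comparisons* agree.
- Replace the control-arm clause in the Results sentence with the week 2 between-arm differences.
- Keep within-arm results only as mean change with CI, labelled descriptive and without p-values. This removes 2 arms × 6 outcomes × 3 visit pairs = 36 tests.
- State the number analysed in each arm, since the degrees of freedom imply 43 rather than 46.

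The cost is a re-analysis of data already collected and a rewritten results section. No new data are needed. Baseline adjustment uses one degree of freedom per model and usually gains precision.

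### The Conclusion treats an absence of side effects as confirming that ESWT is safe, but an arm of 23 patients with no described safety assessment cannot support that.

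*Combined protocol and SAP*

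**What the plan says.** The Conclusion says that ESWT gave the better results "without any side effects confirming the safety and efficiency of ESWT in cervical myofascial pain". This goes further than reporting that no events were seen, because it presents their absence as proof of safety.

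The rest of the document is about efficacy:

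- **Objective.** The aim is the effect of shock "wave therapy (ESWT) on cervical myofascial pain in expression of decreasing pain and improving" cervical range of motion. Safety is not mentioned.
- **Outcome measures.** "Pain assessment was measured by visual analogue scale (VAS) and pressure" algometry, and "Cervical range of motion device (CROM) was used for assessment of lateral flexion" and rotation. Measurements are at baseline, 2 weeks and 4 weeks, when the trial ends. Side effects are not listed.
- **Subjects.** The 46 patients were "recruited in this trial and subdivided at random into two equal groups".
- **Results and tables.** The Results text gives no side-effect data. The text describes Table 1 as subject characteristics and Tables 2 and 3 as range of motion, VAS and pressure pain threshold.

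Nowhere does the text define a side effect, say how or when side effects were sought, or give a count or denominator by arm.

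**The concern.** Two things are needed before an absence of events says much about safety: a method that would have found the events, and enough patients for the absence to be informative. The document describes no method, and the ESWT arm is small. Side effects may well have been monitored, but the reader cannot tell. If events were noted only when patients volunteered them, a count of zero supports even less.

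A reader could take the Conclusion to mean that ESWT has been established as safe after neck dissection. The trial had a fair chance of missing a harm that affects 1 patient in 20.

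**Working it through.** The document states no side-effect rate, confidence limit or sample-size calculation, so there is no figure of its own to reproduce. The 95% level is a convention chosen for this check.

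**Inputs**
- Patients: 46 in two equal groups (Subjects), so 46/2 = 23 on ESWT. The document does not print 23.
- Side effects on ESWT: zero, stated in words only (Conclusion).

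**1. Upper limit for 0/n (Clopper-Pearson), n = 23**
- Two-sided 95%: 1 − 0.025^(1/23) = 0.148
- One-sided 95%: 1 − 0.05^(1/23) = 0.122

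**2. Chance of seeing no event in 23 patients, (1 − p)^23**
- True rate 5%: 0.95^23 = 0.307
- True rate 10%: 0.90^23 = 0.089

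**3. Smallest true rate with an 80% chance of at least one event**
- 1 − 0.2^(1/23) = 0.068

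Steps 1 to 3 assume that all 23 patients were observed and every event was captured.

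**4. Comparison with control.** The control count is not stated. If it were also 0/23, the Newcombe 95% interval for the difference would run from about −14.3 to +14.3 percentage points. The half-width is the Wilson upper limit for 0/23, z²/(23 + z²) = 0.143 with z = 1.96.

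**5. Incomplete capture.** The document gives no capture fraction, so the values of s here are assumptions. The limit becomes 0.148/s, and the chance of seeing no event at a 5% true rate becomes (1 − 0.05s)^23.

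| Capture fraction s | Two-sided 95% limit | Chance that a 5% harm goes unseen |
|---|---|---|
| 1 | 14.8% | 31% |
| 0.75 | 19.8% | 42% |
| 0.5 | 29.6% | 56% |

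**6. Fewer than 23 observed.** With 2 groups, 6 outcomes and 3 time points, the Wilks error degrees of freedom are N − 7 for treatment and N − 13 for time and for the interaction. The reported values are 36 and 30, and both give N = 43 (36 + 7 and 30 + 13). With N = 46 they would be 39 and 33. This is the number in the efficacy model, not the safety denominator. If 1, 2 or 3 of the absent patients were in the ESWT arm and also unobserved for safety, which the document does not establish, the two-sided limit is:
- 0/22: 15.4%
- 0/21: 16.1%
- 0/20: 16.8%

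**The case against.** The document is largely a structured summary followed by results. It describes few procedures in detail, so silence on side-effect recording does not show that none took place. That is fair, and nothing here alleges that side effects went unmonitored or that harm occurred. The point does not depend on it, because perfect monitoring of 23 patients still leaves the 14.8% limit.

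The count 0/23 is derived, not reported. This also stands. It assumes that every allocated ESWT patient was observed, and 23 is the most favourable denominator that the stated allocation allows.

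Since zero events fix the lower bound at 0, the one-sided limit of 12.2% is arguably as natural as 14.8%. Both are given, and neither confirms safety.

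The scenarios for incomplete capture, the control arm and the reduced denominator rest on values the document does not supply. They only show how the limit would move, and the conclusion does not need them.

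Finally, the fault lies in one phrase of interpretation in an efficacy trial, and no estimate or test changes. That limits its seriousness. However, the phrase is part of the trial's stated conclusion and claims something that its design and size cannot deliver.

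**Conclusion.** The concern holds. Even if all 23 ESWT patients were observed and every event was captured, zero events is compatible with a true rate of up to 14.8% (two-sided 95%) or 12.2% (one-sided). Only harms with a true rate of 6.8% or more had at least an 80% chance of appearing once. A harm with a 5% rate would more likely than not have been seen, but would be missed about 3 times in 10. Incomplete capture or fewer patients observed would weaken the evidence further. The wording should be changed. The efficacy findings are not affected.

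**What to change.** Replace the safety claim in the Conclusion with a statement of what was observed, along these lines: *no side effects were reported among the n ESWT patients over the 4-week trial (for n = 23, exact two-sided 95% upper limit 14.8%); the trial was not designed to establish safety.* Fill in n as the number actually observed and recompute the limit if it is not 23. If the period over which side effects were observed differs from the 4 weeks, give the actual period.

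Add a short account of how and when side effects were recorded in each arm. Tabulate by arm whatever was recorded for all 46 randomised patients, with the number observed in each arm. If side effects were not systematically sought, say so, and do not present the upper limit as if it came from active surveillance.

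The cost is one sentence, a short description and, where records exist, a small table. No new visits, data collection or efficacy analysis is needed. The safety claim becomes weaker.

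### Post I and post II group comparisons are described without the measured baseline as covariate; adjustment would narrow the intervals if the baseline correlation exceeds about 0.16 in size

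*Combined protocol and SAP*

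**What the plan says.** The Subjects paragraph reports "46 patients with cervical myofascial pain following neck dissection surgery were" recruited and split at random into two equal groups, so 23 per arm. The Outcome measures paragraph says that VAS, pressure algometry and cervical range of motion were all taken before the study, at 2 weeks (post I) and at 4 weeks (post II).

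The Effect of treatment section names one model: "Mixed MANOVA showed a significant interaction effect of treatment and time", with "F (12, 30) = 227.55, p = 0.001". It refers descriptive results to tables whose contents are not in the text available: "Table 2 and 3 showed descriptive statistics of rotation and side bending ROM, VAS and PTT".

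The Between group comparisons section takes each visit separately. For the pre visit: "Pre-trial evaluations revealed non statistical difference between both study and control groups in all measured variables (p > 0.05". For range of motion and pressure pain threshold, the improvement "was reported at post I and II in the study group compared to control group (p > 0.001". The Results paragraph gives the same group comparisons as "ESWT Group revealed significant improvement in all parameters at post I and II compared to control group (p < 0.001". The Within group comparison section sets post I and post II against pre inside each arm.

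No baseline covariate or adjusted difference is described. The text has no statistical methods section and does not name the pairwise test.

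**The concern.** As described, the group difference at post I or post II leaves out each patient's own starting value, although that value was collected. In a small trial this can cost in two ways.

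- **Precision.** If baseline predicts follow-up, adjustment removes that part of the residual variance and narrows the interval around the difference.
- **Chance imbalance.** Randomisation balances baseline on average, not in one draw of about 46 patients. A non-significant baseline test does not correct for the imbalance that occurred.

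At stake are the width of each interval and the robustness of each estimated difference. Whether ESWT beat control is not at stake.

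**Working it through.** **Inputs.** From the documents: 46 recruited, equal allocation, six outcomes (rotation in two directions, side bending in two directions, VAS, pressure pain threshold), three visits, and F degrees of freedom (12, 30) and (6, 36). Assumed: the correlation r between baseline and follow-up, common to both arms; equal SDs; two-sided 95% intervals. Widths are in units of the outcome's SD at one visit.

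**1. How baseline enters the MANOVA.** Numerator df 12 = 6 outcomes × 2, so three visits were response levels. Post I and post II alone would give 6 × 1 = 6. The pre visit is therefore in the model as a response, and the interaction uses contrasts of the change-from-pre type. It is one overall test and gives no estimate for any single outcome.

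**2. Number analysed.** For two groups and no covariates, the error df are N − 2 − 6 + 1 = N − 7 (between patients) and N − 2 − 12 + 1 = N − 13 (within patients). The printed 36 and 30 both give N = 43; N = 46 would give 39 and 33. Both sizes are carried forward, with 43 taken as 22 + 21.

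**3. Unadjusted half-width** = t(0.975, N − 2) × √(1/n1 + 1/n2).
- 23 + 23: 2.015 × √(2/23) = 2.015 × 0.295 = 0.594 SD.
- 22 + 21: 2.020 × √(1/22 + 1/21) = 2.020 × 0.305 = 0.616 SD.

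**4. ANCOVA half-width** = t(0.975, N − 3) × √[(1/n1 + 1/n2)(1 − r²)(1 + 1/(N − 4))]. The last factor is the small-sample cost of estimating the slope. Example, 23 + 23 and r = 0.5: 2.017 × √(0.08696 × 0.75 × 1.0238) = 0.521 SD.

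**5. Change-from-pre half-width**, for comparison, = unadjusted × √(2(1 − r)).

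| assumed r | ANCOVA, 23 + 23 | against 0.594 | change from pre, 23 + 23 | ANCOVA, 22 + 21 (against 0.616) |
|---|---|---|---|---|
| 0 | 0.602 | 1.2% wider | 0.840 | 0.624 (1.4% wider) |
| 0.3 | 0.574 | 3% narrower | 0.703 | 0.596 |
| 0.5 | 0.521 | 12% narrower | 0.594 | 0.541 |
| 0.7 | 0.430 | 28% narrower | 0.460 | 0.446 |

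Percentages use unrounded values. Simulation (40,000 runs) gave ratios of mean adjusted to mean unadjusted half-width of 1.012, 0.965, 0.877 and 0.723 for 23 + 23, in agreement.

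**6. Break-even.** Setting the ANCOVA width equal to the unadjusted width gives |r| = √[1 − ((N − 4)/(N − 3)) × (t(0.975, N − 2)/t(0.975, N − 3))²], which is 0.157 for N = 46 and 0.163 for N = 43.

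**7. Is significance at risk?** Two-sided p < 0.001 needs an observed difference above t(0.9995, N − 2) × √(1/n1 + 1/n2): 3.526 × 0.295 = 1.04 SD for 23 + 23, and 3.544 × 0.305 = 1.08 SD for 22 + 21. If the Results paragraph is right, every difference exceeds its 95% half-width by a wide margin.

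**The case against.** The strongest reply is that no error has been shown. Comparing randomised groups at a follow-up visit is valid without a covariate, and adjustment is unlikely to change any significance statement. That stands, and it limits the point to an optional improvement. A reader might infer that the reported effects are biased or doubtful; the documents do not support that.

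A reader might also infer that baseline was ignored. It was not. It is a response level in the MANOVA, it drives the interaction, and the within-group comparisons use it. Only the per-visit group differences are described without it.

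The argument rests partly on silence. With no methods section, no named pairwise test and table contents not shown, a covariate that is not described may still have been used. The printed df would even fit 46 patients with three undescribed covariates. Nor can it be inferred that mean differences went unreported, since the tables may hold them.

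It is tempting to say that adjustment would probably tighten the intervals, because the same patients are measured on the same scale a few weeks apart. The documents give no r, so only the conditional statement can be made.

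A technical objection also stands. A repeated-measures model with one baseline slope for both visits can lose precision at week 4. With assumed r of 0.6 at post I and 0.1 at post II, equal SDs and the average slope of 0.35, the post II residual variance is 1 − 2(0.35)(0.1) + 0.35² = 1.05 times the unadjusted variance. With its own slope it is 1 − 0.1² = 0.99. The model therefore needs a baseline × visit term.

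**Conclusion.** The point holds as one of precision and of handling chance baseline imbalance. The post I and post II group comparisons are described without the baseline that was collected for every outcome. Adjustment pays if |r| exceeds about 0.16. At r = 0.5 the half-width with 23 per arm falls from 0.594 to 0.521 SD. If baseline and follow-up are uncorrelated, the cost is an interval little more than 1% wider.

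These sizes rest on an assumed r common to both arms and on 43 or 46 patients analysed; the choice between those two numbers hardly matters for the relative gain. The statement that significance is safe rests on the p < 0.001 in the Results paragraph. The Between group comparisons section prints p > 0.001 for the same comparisons. That conflict and the 43-against-46 question are separate discrepancies and add no weight to this point.

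**What to change.** First confirm how many patients were analysed in each arm and whether any covariate was used. Then, for each outcome, take one of two routes:

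- an ANCOVA at week 4, and a separate one at week 2, with group and the patient's own baseline value; or
- a repeated-measures model on post I and post II with group, visit, group × visit, baseline and baseline × visit.

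Report the baseline-adjusted difference with its 95% interval, the number analysed per arm and the observed baseline-to-follow-up correlation, so that the gain can be seen. Label the analysis post hoc, because results are already known. If adjustment was in fact used, state it and name the model.

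The cost is wording and a re-run on data already held, with no new patients or visits. The statistical price is at worst about 1.2% to 1.4% in interval width. Because the analysis can only be post hoc, it supplements the reported comparisons and does not replace them.

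### The printed MANOVA degrees of freedom do not fit 46 randomised patients: they imply 43 analysed, or fewer than three absent plus undeclared parameters, or 46 with three undeclared parameters

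*Combined protocol and SAP*

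**What the plan says.** Under Subjects, the document states that "46 patients with cervical myofascial pain following neck dissection surgery were" "recruited in this trial and subdivided at random into two equal groups", which is 23 per arm. Under Outcome measures, it lists VAS, pressure algometry, and lateral flexion and rotation of the neck on both sides. These are measured at baseline, 2 weeks and 4 weeks. That makes six outcomes at three visits.

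The section on the effect of treatment on ROM, VAS and PTT reports one mixed MANOVA with three tests:

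- treatment: "There was a significant main effect of treatment (Wilks' Lambda = 0.03, F (6, 36) = 162.55, p = 0.001"
- time: "There was a significant main effect of time (Wilks' Lambda = 0.005, F (12, 30) = 489.27"
- treatment by time: "Wilks' Lambda = 0.01, F (12, 30) = 227.55"

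No covariate is named. Age, weight, height and sex appear only under Subject characteristics, as a baseline comparison: "There weren't statistical differences (p>0.05) in the mean of age, weight, height and sex distribution between groups". The supplied text gives no number analysed and mentions no dropout, exclusion or missing value.

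**The concern.** The degrees of freedom of a MANOVA follow from the number of patients, groups, outcomes, visits and extra model parameters. They therefore give an independent check on who was analysed and with what model. Here the numerator df agree with the stated design and the denominator df do not agree with the stated sample.

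Each possible explanation leaves something to correct:

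- **43 analysed, no extra parameters.** The efficacy result is not an analysis of all randomised patients, and the effect estimate may carry attrition bias in either direction. Because 43 is odd, the two analysed groups also cannot be equal in size.
- **44 or 45 analysed with one or two extra parameters.** Both the analysis set and the model are undeclared.
- **46 analysed with three extra parameters.** The model is misdescribed, and a reader cannot tell whether the adjustment was planned.
- **46 analysed, no extra parameters.** The degrees of freedom of all three tests are wrong as printed, and the F values need checking.

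**Working it through.** **Inputs.** N = 46 patients and 2 groups (Subjects); p = 6 outcomes and t = 3 visits (Outcome measures). The printed tests are F(6, 36) = 162.55, F(12, 30) = 489.27 and F(12, 30) = 227.55. Let k be the number of extra between-subject parameters. The text declares none, so k = 0.

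**Numerator df.** Treatment: p = 6. Time and interaction: p × (t − 1) = 6 × 2 = 12. Both match the printed values, so the design has been read correctly.

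**Denominator df.** Each hypothesis has one between-subject degree of freedom, so the F transform of Wilks' Lambda is exact:

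df2 = (N − 2 − k) − q + 1, with q = 6 for treatment and q = 12 for time and interaction.

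For N = 46 and k = 0: 44 − 6 + 1 = 39, and 44 − 12 + 1 = 33.

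Working back from the printed values: 36 + 6 − 1 = 41, and 30 + 12 − 1 = 41. All three tests agree on N − 2 − k = 41, so N − k = 43.

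| N | k | Treatment | Time, interaction | Matches print |
|---|---|---|---|---|
| 46 | 0 | F(6, 39) | F(12, 33) | no |
| 46 | 3 | F(6, 36) | F(12, 30) | yes |
| 46 | 4 | F(6, 35) | F(12, 29) | no |
| 45 | 2 | F(6, 36) | F(12, 30) | yes |
| 44 | 1 | F(6, 36) | F(12, 30) | yes |
| 43 | 0 | F(6, 36) | F(12, 30) | yes |

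The rows for N = 46 and for N = 43 were confirmed by fitting a MANOVA to simulated data. Adjusting for all four baseline characteristics with 46 patients does not fit; exactly three parameters would. At N = 46 with k = 0, changing the number of outcomes (4 to 9 tried) does not give the printed pairs.

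**Can the Lambdas decide?** Lambda = 1/(1 + F × df1/df2).

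| Test | Printed Lambda | At printed df | At the df for N = 46, k = 0 |
|---|---|---|---|
| Treatment | 0.03 | 0.0356 | 0.0385 |
| Interaction | 0.01 | 0.0109 | 0.0119 |
| Time | 0.005 | 0.0051 | 0.0056 |

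The treatment value appears to have been truncated rather than rounded. Once truncated, both columns print alike, so the Lambdas do not discriminate. The accompanying 0.98, 0.99 and 0.96, if they are 1 − Lambda, do not discriminate either.

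**Significance.** The largest p among the three printed F values, at either set of df, is 1.5e-24.

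**What three absent patients could do to the effect size.** This applies only if 43 were analysed, and it rests on assumptions that are not in the document: absent patients had zero change, and the control change is a fraction r of the ESWT change, with r from 0 to 0.5. Let a be the number absent from ESWT and b = 3 − a the number absent from control. Adding them back changes the between-arm difference in mean change by

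[(23 − a)/23 − r(23 − b)/23]/(1 − r) − 1.

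| Absent from ESWT / control | r = 0 | r = 0.5 |
|---|---|---|
| 3 / 0 | −13% | −26% |
| 2 / 1 | −9% | −13% |
| 1 / 2 | −4% | 0% |
| 0 / 3 | 0% | +13% |

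If the absent patients changed like their own arm, the shift is 0%.

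**Worst-case look at the treatment F.** A simulation calibrated to F = 162.55 gave absent patients control-like scores. The median F(6, 39) was about 21 (p about 1e-10) if all three were ESWT, 31 if two were and 54 if one was. If none was, it was about 168 to 180, depending on calibration. With all three in ESWT but halfway between the arms, a separate run gave about 70; with all three like their own arm, about 200.

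**The case against.** The arithmetic is not in dispute. The strongest reply is that the document says 46 were recruited and randomised, and nowhere that 46 were analysed. On that reading 43 analysed contradicts nothing and is a reporting omission, which Tables 1 to 3 may resolve. This stands in part: the tables could show which explanation is true. They cannot make 46 patients and the stated model yield the printed df. An analysed set smaller than the randomised one also has to be declared.

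Second, a patient with one missing value among 18 (six outcomes at three visits) drops out of this MANOVA but could still contribute to the per-outcome comparisons. The three may not be lost to follow-up, and the omnibus F is not the effect estimate. This is a fair limit on any claim of bias, and it is a further reason to report numbers by arm and visit.

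Third, the size figures rest on assumptions and cover only one explanation. That is correct. The fall in F to about 21 is an extreme case, because patients scoring like the other arm become gross outliers when separation is this large. The figures are illustrations, not estimates.

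Fourth, three extra parameters need not be three covariates; one four-level factor would also use three df. This is accepted and does not change the result.

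A single misprint is not a plausible defence: three tests with two different denominators are all short by the same three.

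**Conclusion.** The concern holds. Forty-six patients and a model of treatment, time and interaction give F(6, 39) and F(12, 33), while the document prints F(6, 36) once and F(12, 30) twice. Confidence is high for this mismatch. The df cannot identify the cause, the arm, or the reason any patient was absent, and attrition bias is a possibility, not a finding.

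Under the stated assumptions, the between-arm difference could move by anything from −26% to +13% if three patients were left out. No scenario examined removes nominal significance. The point must still be fixed, because these are the only tests reported with df in the supplied text and they support the efficacy conclusion.

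**What to change.** Reconcile the Subjects paragraph with the mixed MANOVA paragraph. State the numbers randomised and analysed per arm and per visit, give the reason for each exclusion, and list every model term. Then, depending on what the data show:

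- **46 analysed, no covariates:** rerun and correct the tests, with df F(6, 39) and F(12, 33).
- **46 analysed with extra parameters:** name them and say whether they were pre-specified.
- **43 analysed:** label the result complete-case, add an analysis of all available data from patients as randomised, and add a sensitivity analysis that varies both the arm and the assumed outcome of the three absent patients.
- **44 or 45 analysed:** do both of the last two.

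The cost is a few sentences, at most one rerun, and one sensitivity analysis on existing data. No new patients or procedures are needed. If the absent patients have no follow-up values, only the sensitivity analysis can address them.
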